This study will have commercial impact in that it will be the first to determine the relative effectiveness of unlimited, asynchronous MBP compared to more traditional VBP. Thus, this study will make a significant public health impact by being the first to evaluate a commercial product delivering MBP compared to VBP and addresses NIMH strategic priority area 4.1 (improve the efficiency and effectiveness of mental health services through research). Second, this study will have an impact on clinical care in that it will be able to determine the best digital treatment algorithm for people who do not respond to either MBP or VBP only and who respond to VBP, MBP, or the combination. There has been considerable interest in the clinical and policy realm in understanding who responds to different levels of care, and when patients should be "stepped up" in intervention intensity. Thus, this study will make a significant clinical impact by identifying a treatment sequence for systems that provide teletherapy and is responsive to NIMH priority area 3.2 (develop ways to tailor existing and new interventions to optimize outcomes).

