1. Test effectiveness of unlimited daily, message-based psychotherapy (MBP) for depression, compared to weekly traditionally delivered, videoconferencing-based psychotherapy (VBP). Level 1 conditions: unlimited MBP and weekly VBP.
2. Develop an evidence-based treatment sequence for those who do not respond to either MBP or VBP. Level 2 conditions for participants who do not respond to treatment: MBP+VBP_{weekly} (switch from MBP to weekly VBP with MBP), MBP+VBP_{monthly} (switch from MBP to monthly VBP with MBP), VBP_{weekly}+MBP (switch from VBP to weekly VBP with MBP), and VBP_{monthly}+MBP (switch from VBP to monthly VBP with MBP).

Hypothesis 1: Compared to those randomized to weekly video care at baseline, patients randomized to message-based care will have greater improvements in depression (1a) and social functioning (1b), be more likely to show a treatment response (1c), and be more likely to experience remission (1d) at 5 and 12 weeks of care. Hypothesis 2: For those who fail to respond to treatment from baseline to 5 weeks, those re-randomized to receive (or retain) weekly video care will have greater improvements in depression and be more likely to show a response to treatment than those randomized to monthly video care. Hypothesis 3 (moderator): Baseline anxiety will moderate improvement in depression such that those with greater anxiety will have better response to message-based care at 5 and 12 weeks than to video-based care. Exploratory Aims: Exploratory evaluation of differences among groups in treatment engagement by week 5, ratings of therapeutic alliance at weeks 4 and 10, ratings of

quality of care and amount helped by treatment at week 10, and ratings of goal satisfaction, plans to continue using treatment, and likelihood to recommend treatment to others at week 12.

Sample Size and Power: We propose to screen 4,789 potential participants, anticipating we will enroll 1,250 participants to arrive at a final sample of 1,000 evaluated participants, assuming a 20% dropout rate by the last assessment. In our previous psychotherapy studies, dropout rates have been on the order of 10% by final assessment. In our recent on-line studies with Google Verily, drop out has been on the order of 20%. Our large incentive arm, tested in Phase 1, is based on the incentive analyses done on the Baseline Mood Study at Verily.

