Level 1 Power: For the quantitative primary outcome (PHQ-9) we have greater than 80% power to detect a 0.20 standard deviation across groups which corresponds to a clinically meaningful small difference. For a binary success indicator, we will consider a 50% reduction in PHQ-9 from baseline to week 5, and we have greater than 80% power to detect an absolute difference of 10% (e.g., 60% of subjects with >50% improvement versus 70% of subjects with >50% improvement).

Level 2 Power: The primary comparison in the second stage is the comparison of the Ultimate Plan (UP; MBP with weekly VBP) versus the Premium Plan (PP; MBP with monthly VBP) for each of the first stage randomization groups (MBP and VBP). We expect a second stage analysis sample of 324 subjects, and this corresponds to 80% power to detect a 0.32 standard deviation difference across the UP and PP groups when pooling across the primary MBP and VBP strata. Our primary second stage analysis will construct an overall UP versus PP difference stratifying on first stage randomization, and secondary analysis will consider the UP versus PP difference within the MBP and VBP groups separately.

Accounting for Provider Effects: Each provider will treat both MBP and VBP patients. Therefore, our primary analyses will all cluster on provider either using linear mixed models or generalized estimating equations to yield valid statistical inference. However, since treatment condition will vary within provider, the impact of provider clustering is to effectively balance or control for provider effects. Therefore, our power calculations are conservative since they do not account for the potential increase in precision associated with control for provider effects. Such within-provider randomization is in contrast to traditional cluster randomized trials where providers treat all patients in one study condition and thus increase variability associated with treatment comparisons through the well-known intra-cluster correlation coefficient.

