Hypothesis	Timepoint(s)	Statistical Test	Contrast/analysis of interest
1a: Compared to those randomized to weekly video care at baseline, patients randomized to message-based care will have greater improvements in depression	Baseline to W5	3-level mixed effects model	MBP vs VBP
1b: Compared to those randomized to weekly video care at baseline, patients randomized to message-based care will have greater improvements in social functioning	Baseline to W12	3-level mixed effects model	MBP vs VBP
1c: Compared to those randomized to weekly video care at baseline, patients randomized to message-based care will be more likely to show a treatment response at 5 and 12 weeks of care.	Between W3 to W5 / W12	Chi-square tests	MBP vs VBP
1d: Compared to those randomized to weekly video care at baseline, patients randomized to message-based care will be more likely to experience remission at 5 and 12 weeks of care.	Between W3 to W5 / W12	Chi-square tests	MBP vs VBP
2: For those who fail to respond to treatment from baseline to 5 weeks, those re-randomized to receive (or retain) weekly video care will have greater improvements in depression than those randomized to monthly video care	W6 to W12	3-level mixed effects model with time centered at week 6	MBP+VBP _{weekly} vs MBP+VBP _{monthly} ; VBP _{weekly} +MBP vs VBP _{monthly} +MBP
2: For those who fail to respond to treatment from baseline to 5 weeks, those re-randomized to receive (or retain) weekly video care will be more likely to show a response to treatment than those randomized to monthly video care	W12	Chi-square test	MBP+VBP _{weekly} vs MBP+VBP _{monthly} ; VBP _{weekly} +MBP vs VBP _{monthly} +MBP
3 (moderator): Baseline anxiety will moderate improvement in depression such that those with greater anxiety will have better response to message-based care at 5 and 12 weeks than to video-based care.	Baseline to W12	3-level mixed effects model, with mean-centered baseline GAD-7	MBP vs VBP

Exploratory: We will explore whether there will be differences among groups in treatment engagement by week 5	Between W3 to W5	Chi-square test	MBP vs VBP
Exploratory: We will explore whether there will be differences among groups in ratings of therapeutic alliance	W4 / W10	2-level mixed effects models	W4: Level 1 conditions (MBP vs VBP); W10: Level 2 conditions (MBP vs VBP; MBP+VBP _{monthly} vs MBP+VBP _{weekly} ; VBP _{monthly} +MBP vs VBP _{monthly} +MBP)

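### The plan gives no estimate of whether the weekly-versus-monthly video effect differs by starting arm, and Table 2 lists only the two within-arm contrasts, which would often disagree by chance when the effects are equal.

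*Combined protocol and SAP*

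**What the plan says.** The Level 2 Power paragraph of section 8.0 gives the sample size and detectable effect: "We expect a second stage analysis sample of 324 subjects, and this corresponds to 80% power to detect a 0.32 standard deviation difference". That figure refers to the UP versus PP comparison with the two starting arms combined. The paragraph then names the main analysis, "Our primary second stage analysis will construct an overall UP versus PP difference stratifying on first stage randomization", and adds that "secondary analysis will consider the UP versus PP difference within the MBP and VBP groups separately". On this wording the pooled difference is primary and the within-arm differences are secondary.

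Two other places pull the other way. The opening sentence of the same paragraph describes the primary UP versus PP comparison as being made "for each of the first stage randomization groups (MBP and VBP"). Table 2, to which the Statistical Analyses paragraph sends the reader for the analysis of each hypothesis, has two Hypothesis 2 rows: PHQ-9 from week 6 to week 12, using a "3-level mixed effects model with time centered at week 6", and response at week 12, using a chi-square test. Both rows list the weekly-versus-monthly contrast among MBP starters and the same contrast among VBP starters. Neither lists a pooled contrast.

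The second Phase 2 goal is "Develop an evidence-based treatment sequence for those who do not respond to either MBP or VBP", and section 1.1 presents "identifying a treatment sequence for systems that provide teletherapy" as the study's clinical impact. No section specifies a Level 1 by Level 2 interaction, a homogeneity test, or a way of reading discordant within-arm results. Benjamini-Hochberg adjustment is planned within Hypothesis 2.

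**The concern.** Anyone building a treatment sequence from this trial will ask whether the better step-up depends on where the patient started. The pooled difference does not answer that, because it is an average over starting arms. The only planned results that bear on the question are two separate tests, each on about half the second-stage sample. One significant result and one non-significant result do not show that the two effects differ. With tests of moderate power, that pattern is common when the effects are identical.

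What is at stake is the trial's intended product. A report showing weekly video to be significantly better in one starting arm only invites a recommendation that differs by starting treatment, without any estimate of the difference on which it would rest.

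**Working it through.** **Inputs.** From section 8.0: second-stage sample 324, detectable effect 0.32 SD, power 80%, pooled over first-stage strata. Not stated, so assumed: two-sided alpha 0.05, 1:1 Level 2 allocation, equal strata (162 each, so 81 versus 81 within each), and a comparison at a single endpoint with SD 1.

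**The plan's own figure.** The pooled comparison is 162 versus 162, with SE = √(1/162 + 1/162) = 0.111. Power at 0.32 SD = Φ(0.32/0.111 − 1.96) = Φ(0.92) = 82.1%, or 81.9% with the noncentral t. The effect detectable with 80% power is 0.311 SD. The stated 80% at 0.32 SD is thus reproduced, slightly conservatively.

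**Within-arm power.** Each stratum has SE = √(1/81 + 1/81) = 0.157. Power at 0.32 SD = Φ(0.32 × √40.5 − 1.96) = Φ(0.076) = 53.0%.

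**Discordance with equal effects, unadjusted.** The strata are independent. With p = 0.530:
- exactly one significant: 2p(1 − p) = 2 × 0.530 × 0.470 = 49.8%
- both: p² = 28.1%
- neither: (1 − p)² = 22.0%

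**With Benjamini-Hochberg over the two contrasts.** Both are declared if both p-values are at most 0.05; otherwise only one at or below 0.025 is declared. Power at 0.025 is Φ(2.036 − 2.241) = 41.9%. Exactly one is declared with probability 2 × 0.419 × 0.470 = 39.3%. In a four-test family (two arms by two outcomes) the figure is about 37% to 39%, assuming a correlation of 0.6 to 0.8 between outcomes and a response-test signal 0.8 to 1.0 times that for PHQ-9.

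**Dependence on the common true effect.**

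| True effect in both arms | Within-arm power | Exactly one significant, unadjusted | Exactly one, Benjamini-Hochberg over two |
|---|---|---|---|
| 0.20 SD | 24.6% | 37% | 2 × 0.166 × 0.754 = 25% |
| 0.32 SD | 53.0% | 50% | 39% |
| 0.40 SD | 72.1% | 40% | 2 × 0.620 × 0.279 = 35% |
| 0.50 SD | 88.9% | 20% | 2 × 0.827 × 0.111 = 18% |

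Unequal strata matter little: at 0.32 SD unadjusted, a 185/139 split gives 50.5% and a 210/114 split gives 52.8%.

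**Does a significant pooled result protect the reader?** No. In simulation at a common 0.32 SD, the pooled test is significant and exactly one arm is nominally significant in 45.9% of trials. Divided by pooled power of 82.1%, that is 56% of the trials with a significant pooled result.

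**What the direct comparison can show.** The difference between the two within-arm effects has SE = √(4/81) = 0.222 SD and a 95% half-width of 1.96 × 0.222 = 0.44 SD. Power for a true difference of 0.32 SD is Φ(0.32/0.222 − 1.96) = 30%. Power of 80% needs a difference of (1.96 + 0.842) × 0.222 = 0.62 SD. With equal effects, one-arm-only significance together with a significant interaction occurs in about 5% of trials, against about 50% for one-arm-only significance alone.

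**The case against.** The strongest reply is that the plan already has a pooled, stratified primary analysis, powered as such, and labels the within-arm comparisons secondary. That stands. A reader of Table 2 alone might infer that no pooled analysis is planned, but the Level 2 Power paragraph rules this out. It does not supply the missing estimate, because a pooled difference says nothing about variation between starting arms.

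Second, the plan commits to no arm-specific claim. The second aim in section 1.2 and Hypothesis 2 ask whether weekly or monthly video is better for non-responders; neither predicts a different answer by starting arm, and nothing says that significance in one arm only will be read as such. This also stands: the harm is a misreading that the plan leaves open, not one that it prescribes. Confidence intervals are promised, so both estimates would be visible, though not the interval for their difference.

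Third, the Table 2 column names contrasts of interest and need not list every model term. Even the moderator row for Hypothesis 3 does not write out its interaction. Two separate model fits are therefore not established. It remains that no comparison of the two effects is specified anywhere.

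Fourth, section 3.0 labels the choice differently by starting arm: augmentation versus minimal augmentation for MBP starters, augmentation versus switch for VBP starters. Within-arm estimates are a legitimate secondary output and should be kept.

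Finally, an interaction test would be weak. That is true, and it argues for showing the estimate with its interval. It also means that a non-significant interaction cannot be used to declare the pooled result valid for both arms.

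**Conclusion.** The point holds as a gap in the secondary analysis and in Table 2; the primary Level 2 analysis is not in question. No section plans an estimate of whether the step-up effect differs by starting arm, and the contrasts that Table 2 does list would often disagree by chance.

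It is tempting to say that equal effects would look arm-specific half the time. The documents do not support that without conditions. About 50% is the unadjusted figure at a true 0.32 SD in both arms, and is close to the maximum of 2p(1 − p). Under the planned Benjamini-Hochberg step over two contrasts it is about 39%, and both figures fall for smaller or larger effects. All rest on the assumed alpha, allocation, equal strata and single-endpoint comparison. The planned repeated-measures model could raise within-arm power and change them. The chance of a discordant pair remains substantial for common effects of 0.20 to 0.40 SD: 37% to 50% unadjusted, and 25% to 39% adjusted, at the values tabulated.

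**What to change.** - For each Hypothesis 2 outcome, fit one model to all re-randomised participants with Level 1 arm, Level 2 condition, time (for PHQ-9) and their interactions.
- Report the pooled weekly-versus-monthly difference, both within-arm estimates, and the difference between the two with its 95% CI. For PHQ-9, expect an SE of about 0.22 SD and a half-width of about 0.44 SD under the assumptions above.
- State that any arm-specific conclusion will rest on that difference and its interval, not on significance in one arm only.
- State that the interaction has low power (about 30% for 0.32 SD, and 80% only at about 0.62 SD), so a non-significant result does not show equal effects.
- Add the pooled contrast to both Hypothesis 2 rows of Table 2, and reconcile the opening sentence of the Level 2 Power paragraph with the later one that names the pooled analysis as primary.

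The cost is an added interaction in each model and a few sentences in the SAP, with no new data or participants. The downside is that fewer arm-specific claims will be possible.

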Statistical Analyses: See Table 2 for analyses by hypothesis. Treatment disengagement, treatment response, and remission will be analyzed using chi-square tests and Cramér V effect sizes. 2-level linear mixed effects models using full information maximum likelihood (FIML) and an unstructured covariance matrix with client nested within clinician will be used for analyses at a single timepoint. Models predicting binary outcomes at a single timepoint will be evaluated using 2-level logistic regression models with Cholesky factorization with client nested within clinician, with Level 2 condition as the independent variable. Effect sizes for these models will be computed via pooled standard deviations of conditions at that timepoint.

Models assessing changes across time will be evaluated using 3-level mixed effects regression models with timepoint nested within client nested within clinician using FIML and an unstructured covariance matrix. Client-level effects will be allowed to randomly vary, and clinician will be a clustering variable with condition approximately balanced within clinicians. Analyses with time from baseline to week 12 will include a spline variable to account for differences in outcome trajectories from baseline to week 5 and from week 6 to week 12.

The mixed-effects models will utilize all available data. Prior research has demonstrated equivalence of longitudinal mixed model analyses using imputed versus non-imputed data (e.g., between multiple imputation and FIML).¹³ Theoretically, there is no reason to expect substantial differences between FIML and MI with a reasonable sample size and complete predictors.¹⁴ Thus, missing data will not be imputed. Cohen's *d* clinical outcome effect sizes for the model predicting PHQ-9 scores by Level 2 condition from weeks 6 to 12 will be computed as the difference between model-estimated means divided by the pooled standard deviations when the second condition

was assigned at week 6. All remaining clinical outcome effect sizes will be computed as the difference between model-estimated means divided by the pooled baseline standard deviations.

We will use the Benjamini-Hochberg procedure to account for Type 1 error by adjusting for familywise error within hypothesis families (e.g., within Hypotheses 1a to 1d; within Hypothesis 2). *P* values and effect sizes with 95% confidence intervals will be reported, as appropriate.¹⁵

Table 2. Analyses by Hypothesis

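### The week-12 chi-square tests of response and remission have no rule for missing outcomes, and the stated reason for not imputing covers only the mixed models

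*Combined protocol and SAP*

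**What the plan says.** Section 8.0, Statistical Analyses, sets the binary tests: "Treatment disengagement, treatment response, and remission will be analyzed using chi-square tests". Table 2 repeats this for three sets of tests:

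- 1c, that message-based care "will be more likely to show a treatment response at 5 and 12 weeks of care", and 1d (remission), each in a week 3 to week 5 window and at week 12;
- the second Hypothesis 2 row, that those re-randomised to "weekly video care will be more likely to show a response to treatment than those randomized to monthly video care", at week 12 only.

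The Phase 2 missing-data text is one paragraph in the same section. It says that the mixed-effects models use every available observation, then gives its reason, "Prior research has demonstrated equivalence of longitudinal mixed model analyses using imputed versus non-imputed data", and concludes: "Thus, missing data will not be imputed". Section 8.0 gives no missing-as-non-response rule, weighting or sensitivity analysis for the chi-square tests.

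Under Sample Size and Power the plan expects to enrol 1,250 and evaluate 1,000, with 20% lost by the last assessment. It adds that the team's earlier psychotherapy studies lost about 10%. Section 5.1 gives a 3-day window for each weekly assessment and ends all study procedures for anyone withdrawn because they need a higher level of psychiatric care.

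**The concern.** The premise is about mixed models and the conclusion is about all missing data. A mixed model fitted by full-information maximum likelihood uses the weekly scores of a person who leaves at week 8. A chi-square test at week 12 has no place for that person. The planned loss is one participant in five, and some of it, such as withdrawal to a higher level of care, is plausibly related to depression outcome. The arms make different demands on participants who know their modality, so equal dropout cannot be presumed.

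If people who leave respond less often than those who stay, observed response rates are too high. If the arms also differ in how many leave, or in who leaves, the comparison between arms is distorted. For Hypothesis 2, the companion analysis is a "3-level mixed effects model with time centered at week 6". It keeps dropouts' scores while the response test discards them, so the two could disagree for that reason alone.

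**Working it through.** **The plan's own figures.** Enrolment: 1,000/(1 − 0.20) = 1,250. Binary power for 60% vs 70% with 500 per arm (two-sided 0.05 and 1:1 allocation assumed): null SE = √(0.65 × 0.35 × 2/500) = 0.0302; alternative SE = √((0.24 + 0.21)/500) = 0.0300; power = Φ((0.10 − 1.96 × 0.0302)/0.0300) = 91.3%, in line with the stated figure of more than 80%. Both reproduce.

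**Inputs for the illustration.** From the plan: 1,250 enrolled, so 625 per arm; 20% average dropout, or about 10% as in the earlier studies; 60% response, the lower rate in the plan's week-5 power example, borrowed here for week 12. Assumed: how dropout divides between the arms, and the true response rate among dropouts. The 0.0125 level is 0.05/4, the strictest Benjamini-Hochberg step for four tests.

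**Formula.** With true response p, dropout d and response q among dropouts, the observed-case rate is (p − d·q)/(1 − d). The test is a two-sided pooled-variance z-test, equivalent to the chi-square.

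**Main case, no true difference, d = 15% vs 25%, q = 40%.**
- Arm A: (0.60 − 0.15 × 0.40)/0.85 = 0.54/0.85 = 63.5%, n = 531.
- Arm B: (0.60 − 0.25 × 0.40)/0.75 = 0.50/0.75 = 66.7%, n = 469.
- Difference 3.1 points; null SE 0.0302, alternative SE 0.0302.
- Upper tail: (1.96 × 0.0302 − 0.0314)/0.0302 = 0.92, probability 0.178. Lower tail 0.001. Total 18%.

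Other cases by the same formula, true response 60% in both arms:

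| Dropout | Response among dropouts | Observed rates | Gap (points) | Rejection at 0.05 | At 0.0125 |
|---|---|---|---|---|---|
| 15% vs 25% | 40% | 63.5% vs 66.7% | 3.1 | 18% | 7% |
| 7.5% vs 12.5% | 40% | 61.6% vs 62.9% | 1.2 | 7% | 2% |
| 15% vs 25% (stress case) | 25% | 66.2% vs 71.7% | 5.5 | 46% | 26% |
| 20% vs 20% | 40% | 65.0% vs 65.0% | 0 | 5% | 1.25% |
| 15% vs 25% | 60% | 60.0% vs 60.0% | 0 | 5% | 1.25% |

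**Equal dropout, different mechanism.** Assume week-5 response of 50% in both arms, and week-12 response of 80% in week-5 responders and 40% in non-responders, so the true week-12 rate is 60%. In one arm, 30% of week-5 non-responders and 10% of responders go missing; in the other, 20% of each. Total dropout is 20% in both.
- First arm, observed: (0.5 × 0.7 × 0.4 + 0.5 × 0.9 × 0.8)/0.8 = 0.50/0.80 = 62.5%. Second arm: 60.0%.
- Gap 2.5 points; simulated false rejection 12.9%.
- Weighting by each arm's full week-5 distribution: 0.5 × 0.4 + 0.5 × 0.8 = 60.0% in both arms, gap zero.

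When missingness depends on scores already observed, as here, using those scores removes the bias.

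**Hypothesis 2.** The plan expects 324 in the second-stage analysis, so 162 per group pooled and 81 within one Level 1 arm; if 324 is counted after 20% loss, 324/0.8 = 405, or about 203 and 101. Assume 40% true response, 15% among dropouts, and 15% vs 25% dropout: (0.40 − 0.0225)/0.85 = 44.4% and (0.40 − 0.0375)/0.75 = 48.3%. The gap is 3.9 points. Because groups are small, rejection is only 7% to 11% at 0.05 and 2% to 4% at 0.0125.

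**The case against.** The strongest reply has four parts.

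*The powered outcomes are elsewhere.* Level 1 Power covers quantitative PHQ-9 and response from baseline to week 5; Level 2 is powered on a standard-deviation difference. Week 5 is less exposed because any PHQ-9 from weeks 3 to 5 can serve. This stands. The point is confined mainly to unpowered week-12 tests, although the plan lists them as tests of its hypotheses.

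*The effect may be small.* At about 10% dropout with a 5-point imbalance the gap is 1.2 points, and equal dropout with one mechanism creates no false difference. People who merely stop care continue to receive surveys (section 5.1), which limits loss. This also stands, but the plan itself budgets for 20%. The planned comparison of treatment disengagement shows only in part whether missing outcomes differ by arm.

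*A likelihood-based week-12 comparison already exists.* A reader might infer from Table 2 that the plan has none at Level 1, because 1a is listed only to week 5. The documents do not support so strong a reading: the text of Hypothesis 1 states improvement in depression at both 5 and 12 weeks, and the Hypothesis 3 model runs to week 12. It remains true that Table 2 lists no Level 1 main-effect test of depression at week 12 other than 1c and 1d.

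*The plan never says complete cases.* Correct. That is inferred from a single-timepoint test combined with no imputation. The therapist-rated CGI-I fallback in section 3.0 serves only the Level 2 randomisation decision and is not named as an outcome for these tests.

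**Conclusion.** The point holds as a gap in the plan. The reason for not imputing does not reach the chi-square tests, and nothing else says how a participant without a week-12 PHQ-9 enters them. It should be fixed, but it does not undermine the powered analyses.

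A reader might go further and infer that the week-12 results will be biased, or that false positives near 46% are to be expected. The documents do not support that. Dropout by arm and response among dropouts are not given. With no true difference, bias needs missingness related to outcome, plus a rate or a relation that differs by arm. Under the assumptions shown, the range runs from zero, through 1.2 points and 7% rejection, to 3.1 points and 18%, with 5.5 points and 46% as a stress case. For scale, the binary difference used in the week-5 power statement is 10 points. The 0.05 rejection rates are unadjusted, so they are upper limits once the Benjamini-Hochberg procedure is applied.

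**What to change.** In section 8.0, Statistical Analyses, limit the no-imputation statement to the mixed models. For 1c, 1d and Hypothesis 2 response, in the text and in Table 2:

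- Analyse all randomised participants (all re-randomised for Hypothesis 2), leaving out only those removed as fraudulent. Report those removals by arm, because under sections 4.4 and 5.1 they are discretionary and can follow the start of treatment.
- Multiply impute missing PHQ-9 from baseline, weekly and three-weekly Talkspace scores, then dichotomise and compare arms.
- Impute within Level 1 arm through week 5. After week 5, impute by treatment path: continuing responder, or assigned Level 2 condition. If the Level 2 cells are too small for separate models, use one model with condition terms.
- For people who leave before Level 2, impute within Level 1 arm and state how their later path is handled.
- Keep the observed-case chi-square and add a tipping-point analysis, both as sensitivity analyses. Report missing outcomes by arm.

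Counting missing as non-response is not a safe substitute. In the main case it gives 0.60 − 0.15 × 0.40 = 54% vs 0.60 − 0.25 × 0.40 = 50%, a false gap of 4 points in the other direction with 29% rejection at 0.05.

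The cost is SAP wording and modest programming. No new data are needed, since all the scores are already collected. The downside is reliance on a missing-at-random assumption, which the tipping-point analysis probes.

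### Cramér V, the only effect size named for response, remission and disengagement, has no sign and no percentage-point scale, although the response and remission hypotheses are directional and week-5 response is powered on a 10-point difference

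*Combined protocol and SAP*

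**What the plan says.** All references are to Section 8.0 (Statistical Analysis Plan) of the combined protocol and SAP.

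- **Effect size.** Under Statistical Analyses: "Treatment disengagement, treatment response, and remission will be analyzed using chi-square tests and Cramér V effect sizes". Table 2 lists only chi-square tests for 1c, 1d, the Hypothesis 2 response and week-5 engagement.
- **Intervals.** The same subsection says that P "values and effect sizes with 95% confidence intervals will be reported, as appropriate". No interval method is given for V.
- **Direction.** Hypothesis 1 expects messaging patients to "be more likely to show a treatment response (1c), and be more likely to experience remission (1d"). Hypothesis 2 expects weekly video to give more responders than monthly video among non-responders. Engagement is exploratory and has no stated direction.
- **Power.** Level 1 Power makes two statements. For PHQ-9, the quantitative primary outcome: "we have greater than 80% power to detect a 0.20 standard deviation across groups". For response: "For a binary success indicator, we will consider a 50% reduction in PHQ-9 from baseline to week 5", and then "we have greater than 80% power to detect an absolute difference of 10% (e.g., 60% of subjects with >50% improvement versus 70% of subjects".
- **Other binary models.** Two-level logistic regression is described, but with Level 2 condition as the predictor, and Table 2 assigns it only to the week-12 exploratory ratings.
- **Clustering.** Accounting for Provider Effects says that all primary analyses will cluster on provider, by mixed models or GEE.

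**The concern.** In a 2×2 table V is the absolute value of the association, so a result that supports 1c and one that contradicts it by the same amount give the same effect size and the same interval. The continuous outcomes in the same hypothesis family, PHQ-9 and social functioning, do get a signed effect: a difference in model-estimated means over a pooled standard deviation.

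The scale is also a problem. The plan states the response effect worth detecting in percentage points, while V depends on the base rate as well as on the gap. A reader cannot set V beside the 10 points without converting it, and cannot compare V for response with V for an outcome of different frequency.

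At stake is the estimate and its interval for the binary hypotheses. When a result is not significant, a reader wants to know how far it could favour either arm. As planned, the reported effect size gives one undirected number.

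**Working it through.** **Inputs.** 1,000 evaluated participants, and 60% versus 70% for week-5 response (Section 8.0). The allocation ratio is not given as a number, so 1:1 (500 per arm) is assumed. Alpha is not stated, so two-sided 0.05 is assumed, in line with the 95% intervals. The interval for V is obtained by inverting the noncentral chi-square distribution, also an assumption. Provider clustering is ignored in these illustrations.

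**1. The plan's own figure.** Power for 60% versus 70% at 500 per arm:

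z = [0.10 − 1.96·√(2·0.65·0.35/500)] / √[(0.24 + 0.21)/500] = (0.10 − 0.0591)/0.0300 = 1.36, so power is 0.913.

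At 400 per arm it is 0.844. The claim of more than 80% is reproduced.

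**2. Loss of sign.** With equal arms of n and mean rate p̄:

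χ² = (p₁ − p₂)² / [p̄(1 − p̄)·2/n], and V = √(χ²/2n) = |p₁ − p₂| / [2√(p̄(1 − p̄))].

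For 70% versus 60%: χ² = 0.01/(0.65·0.35·2/500) = 10.99, p = 0.0009, V = √(10.99/1000) = 0.105.

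For the signed difference the Newcombe interval uses the Wilson limits of each arm, 65.8% to 73.9% for 70% and 55.6% to 64.2% for 60%:

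- lower: 0.10 − √[(0.700 − 0.6584)² + (0.6420 − 0.600)²] = 0.041
- upper: 0.10 + √[(0.7385 − 0.700)² + (0.600 − 0.5565)²] = 0.158

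| MBP | VBP | V (95% interval) | MBP − VBP, points (95% Newcombe) |
|---|---|---|---|
| 70% | 60% | 0.105 (0.043 to 0.167) | +10.0 (+4.1 to +15.8) |
| 60% | 70% | 0.105 (0.043 to 0.167) | −10.0 (−15.8 to −4.1) |
| 64% | 62% | 0.021 (0 to 0.082) | +2.0 (−4.0 to +8.0) |
| 62% | 64% | 0.021 (0 to 0.082) | −2.0 (−8.0 to +4.0) |

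The first two rows have identical V output, and so do the last two.

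**3. What V still tells the reader.** Rearranged, |p₁ − p₂| = V·2√(p̄(1 − p̄)). For 64% versus 62%, p̄ = 0.63 and the factor is 0.966, so the upper limit converts to 0.082 × 0.966 = 0.080, or 8 points. That agrees with the far limit of the signed interval. For 60/70 the factor is 0.954, and the V interval converts to 4.1 to 15.9 points. The size of the gap is therefore bounded. What is lost is which side the 8 points lie on: in the last two rows messaging could be up to 4 points worse or up to 8, and V does not distinguish them.

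**4. Dependence on the base rate.** The same 10-point gap gives:

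| Rates | V |
|---|---|
| 45/55 | 0.100 |
| 60/70 | 0.105 |
| 10/20 | 0.140 |
| 5/15 | 0.167 |

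Conversely, V = 0.105 means 0.105 × 2√(0.1·0.9) = 6.3 points at a mean rate of 10%, and 10.5 points at 50%.

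**The case against.** **The size is recoverable.** With the overall rate in hand, V's limits convert back to points and match the risk-difference limits closely (step 3). This stands. A reader might infer that V's interval sets no limit on a disadvantage of messaging, or that a null result cannot be compared with 10 points at all. The arithmetic does not support either. The loss is of sign and of asymmetry, and the conversion is left to the reader.

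**Raw percentages will show direction.** They probably would, but the plan does not commit to reporting them for these outcomes, and two percentages alone give no interval for their difference.

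**An interval for V is not firmly promised.** The reporting sentence is qualified by appropriateness, and no method is named. This stands in part. A reader might go further and infer that a resampled interval for V would sit above zero and suggest a false association. Nothing in the plan says that resampling will be used, so the point does not rest on that.

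**The trial is not powered mainly on 10 points.** Correct. PHQ-9 at 0.20 SD is the quantitative primary outcome, and the 10 points concern week-5 response only. The scale mismatch is documented for that outcome and not for remission, disengagement, week 12 or Hypothesis 2.

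**The hypotheses are of superiority.** No noninferiority margin is stated, so bounding harm is not a formal objective. That limits the weight of the point, but a directional hypothesis still calls for a directional estimate. For Hypothesis 2 the direction is weekly against monthly video, not messaging against video.

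**Conclusion.** The point holds as a weakness in estimation and reporting. The only effect size named for response, remission and disengagement cannot distinguish a 10-point advantage from a 10-point disadvantage (V = 0.105 in both cases at 500 per arm). It is also not on the scale of the plan's own week-5 response target. The loss of sign affects every outcome listed and matters most for 1c, 1d and the Hypothesis 2 response, where a direction is stated.

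It should not be read as a fault in the chi-square tests, their p-values, the multiplicity procedure or the stated power, which was reproduced. The figures assume 1:1 allocation, two-sided 0.05, a noncentral chi-square interval for V and no clustering. The identity of V under reversal of the arms depends on none of these.

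**What to change.** In Section 8.0, Statistical Analyses, keep the chi-square p-value and change the reported effect:

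- **Main effect:** the signed difference in proportions with a two-sided 95% confidence interval. It should preferably come from a model or GEE that clusters on provider, as Accounting for Provider Effects requires, with the Newcombe interval as an unclustered check.
- **1c, 1d and disengagement:** MBP minus VBP.
- **Hypothesis 2 response:** weekly minus monthly video, pooled and stratified by Level 1 arm (the primary second-stage analysis under Level 2 Power), and also within each Level 1 arm (the contrasts in Table 2).
- **Reading:** set the week-5 response interval against the 10-point difference in Level 1 Power.
- **Cramér V:** keep only as a descriptive extra.

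The cost is a few sentences of SAP wording and one additional model per binary outcome, with no new data and no change to the planned test or its power. Because a clustered interval and an unclustered chi-square p-value can disagree near the significance threshold, the SAP should also say which one governs the conclusion.
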